2.4 Multiplicity Adjustment

If the primary endpoint is statistically significant (two-sided $P < 0.05$), key secondary endpoints will be evaluated with a fixed-sequence testing procedure to control the family-wise type I error rate. Each endpoint will be tested at a two-sided α of 0.05, and testing will proceed down the hierarchy only while significance is maintained.

Testing hierarchy

- a) Week 6 responder rate for PACs ($\geq 50\%$ reduction).
- b) Change from baseline to Week 6 in NSAT burden.
- c) Cumulative incidence of new-onset AF from baseline to Week 8.
- d) Incidence of new-onset AF at Week 4.
- e) Incidence of new-onset AF at Week 6.
- f) Incidence of new-onset AF at Week 8.

If any endpoint fails to achieve significance, formal hypothesis testing will stop, and all remaining secondary endpoints will be summarized descriptively.

3. Data Handling Principles

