4.2.2 Secondary Efficacy Endpoint Analysis

All secondary efficacy end points will be evaluated in the FAS. Missing data for secondary end points will not be imputed.

- **Continuous Endpoints** At each scheduled visit, analyses will be based exclusively on observed values (observed-cases approach); participants lacking data at a given visit will be omitted from that visit's analysis.

- **Categorical Endpoints** Participants with missing data will be classified as non-responders—that is, as not having met the specified end point.

a) The change from baseline in the 24-hour mean number and burden of PACs at Weeks

4, 6, and 8;

- b) The change from baseline in the 24-hour mean episode count and burden of NSAT at Weeks 4, 6, and 8;
- c) The change from baseline in the 24-hour mean episode count of SAT, AF, and AFL at Weeks 4, 6, and 8;
- d) The proportion of participants with new-onset SAT, AF, or AFL lasting \geq 30 seconds during a continuous 72-hour monitoring period at Weeks 4, 6, and 8. This endpoint will be calculated based on the first occurrence of SAT, AF, or AFL during the respective 72-hour monitoring windows;
- e) The cumulative incidence of new-onset AF from baseline to Week 8: The proportion of participants who experience their first episode of AF lasting \geq 30 seconds during any of the 4th, 6th, or 8th-week follow-up windows, with each participant counted only once, even if they have multiple occurrences across different follow-up windows;
- f) The change from baseline in the SF-36 quality of life score at Week 6;
- g) The responder rate for PACs or NSAT will be calculated at Weeks 4, 6, and 8 and compared between the memantine and placebo groups. A PAC responder is defined as a participant whose 24-hour mean PAC count is reduced by \geq 50% from baseline after treatment, and an NSAT responder is defined as a participant whose 24-hour mean NSAT burden is reduced by \geq 50% from baseline after treatment.

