 - For categorical end points, counts and proportions will be summarized by treatment group. Two-sided 95% CIs for incidence, cumulative incidence, or response rate will be calculated with the Clopper – Pearson method. The absolute risk reduction (ARR = incidence in the memantine group – incidence in the placebo group) will be reported, and between-group differences will be tested with a stratified Cochran – Mantel – Haenszel χ^2 test that uses the randomization strata—age (\geq 65 vs. $<$ 65 yr) and baseline PAC count (\geq 5000 vs. $<$ 5000 beats/24 h)—as stratification factors. The relative risk (RR = incidence in the memantine group \div incidence in the placebo group) and its 95% CI, together with the number needed to treat (NNT = $1/|ARR|$), will also be presented.
 - For continuous end points—including the change from baseline at weeks 4, 6, and 8 in the 24-hour mean PAC count and burden; the episode count and burden of NSAT; the

episode count of SAT, AF, and AFL; and the change from baseline to week 6 in the total SF-36 score—an ANCOVA will be fitted. The model will include treatment group as a fixed effect and age and the baseline value of the respective end point as covariates. For each end point, the least-squares mean difference between groups, its two-sided 95% CI, and the corresponding p value will be reported.

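### SAP 4.2.2 calls memantine minus placebo incidence an absolute risk reduction and removes the sign from the NNT, so both figures mislead on direction for the SAT, AF and AFL end points

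*SAP*

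**What the plan says.** The rule is in SAP 4.2.2 and covers all categorical end points alike: "For categorical end points, counts and proportions will be summarized by treatment group", and then "The absolute risk reduction (ARR = incidence in the memantine group – incidence in the placebo group) will be reported". The NNT follows from it: "together with the number needed to treat (NNT = $1/|ARR|$), will also be presented". The relative risk has the same orientation, with memantine on top ("The relative risk (RR = incidence in the memantine group", divided by the placebo incidence), and is to be given with a 95% CI.

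The end points under this one rule have opposite favourable directions. Some count harmful events: the proportions with new-onset SAT, AF or AFL at each monitoring window, and "The cumulative incidence of new-onset AF from baseline to Week 8". Others count favourable events: "The responder rate for PACs or NSAT will be calculated at Weeks 4, 6, and 8 and compared between the memantine and placebo groups".

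SAP 2.4 puts the PAC responder rate first in the fixed sequence and NSAT burden second. The other four places go to AF, beginning with "Cumulative incidence of new-onset AF from baseline to Week 8" and continuing with AF at each of the three recording weeks. The protocol gives no competing definition of ARR or NNT, and protocol 7.3.2 lets the SAP prevail where the two differ.

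**The concern.** A risk reduction is understood as control risk minus treated risk, so that a positive value means fewer events on treatment. The SAP subtracts the other way and keeps the name. For AF, the quantity labelled a reduction is the increase on memantine. The SAP also departs from its own habit: section 3.1.1 defines change as baseline minus post-baseline, so that a positive number there does mean a fall.

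Taking the absolute value then removes the sign from the NNT, and no rule says whether a given NNT is to benefit or to harm. The difference has no planned interval either. Clopper-Pearson is specified for the rates in each arm, and the between-group CI is specified for the RR only.

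What is at stake is how two figures would be read. An abstract or summary table that lifted the ARR and NNT for AF without the neighbouring columns could present harm as benefit, or benefit as harm.

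**Working it through.** The documents state no ARR, NNT or AF rate, so there is no figure of the plan to reproduce. The check applies the formulas as written.

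**Inputs**
- ARR = p(memantine) - p(placebo), NNT = 1/|ARR| and RR = p(memantine)/p(placebo), all from SAP 4.2.2.
- 128 participants per arm, from SAP 1.3.1. The full 128 is used because SAP 4.2.2 counts participants with missing categorical data as not having met the end point, so they stay in the denominator. This assumes that everyone randomised takes a dose.
- All event counts are assumptions, chosen to span a range.

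**AF, formulas as written**

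| Assumed counts, memantine vs placebo | Incidences | ARR as defined | NNT as defined | RR |
|---|---|---|---|---|
| 10/128 vs 4/128 (harm) | 7.81% vs 3.13% | +4.69 points | 21.3 | 2.50 |
| 4/128 vs 10/128 (benefit) | 3.13% vs 7.81% | -4.69 points | 21.3 | 0.40 |
| 3/128 vs 2/128 (small excess) | 2.34% vs 1.56% | +0.78 points | 128 | 1.50 |
| 20/128 vs 10/128 (large excess) | 15.63% vs 7.81% | +7.81 points | 12.8 | 2.00 |

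First row: (10 - 4)/128 = 0.0469 and 128/6 = 21.3. The second row reverses the counts: the sign flips and the NNT does not move. The wrong sign follows from the formula and does not depend on the rates chosen.

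**AF, conventional direction (placebo minus memantine)**
- 10/128 vs 4/128: (4 - 10)/128 = -4.69 points, number needed to harm 21.3.
- 4/128 vs 10/128: (10 - 4)/128 = +4.69 points, number needed to benefit 21.3.

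The two opposite results can now be told apart.

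**Responder rate, formula as written**
- Assumed 64/128 vs 38/128: 50.0% - 29.7% = +20.3 points, NNT = 128/26 = 4.9.
- Here a positive value does mean benefit, so only the name is wrong: a higher response rate is not a risk reduction.

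**What an interval would add**
- For 10/128 vs 4/128, a simple Wald standard error is √(0.0781 × 0.9219/128 + 0.0313 × 0.9688/128) = 0.0283.
- The 95% CI is 0.0469 ± 1.96 × 0.0283, or about -0.9 to +10.2 points (memantine minus placebo).
- An NNT of 21 printed alone would not show that these data leave the direction open.

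**The case against.** The strongest reply is that nobody who reads the whole table need be misled. The same paragraph of SAP 4.2.2 requires counts and proportions by arm and an RR with its CI. In the harm row above, the reader would also see 7.8% against 3.1% and an RR of 2.50; in the benefit row, the reverse and 0.40. Memantine minus placebo is a legitimate, consistently oriented risk difference whose formula is printed in the plan. This largely stands, and it limits the weight of the point. It does not rescue the label for the AF-type end points or the unsigned NNT, which say the wrong thing or nothing about direction when read by themselves.

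Three stronger readings are tempting, and the documents do not support them.
- A reader might infer that the AF tests or the fixed sequence are compromised. They are not: SAP 2.4 runs on p values, which for categorical end points come from the stratified CMH test, and neither ARR nor NNT enters it.
- A reader might infer that all the categorical effect measures carry the wrong sign. The RR is correctly oriented throughout, and the difference has the right sign for the PAC and NSAT responder rates, the first of which heads the hierarchy.
- A reader might infer that an unstratified difference beside a stratified test is an error. The SAP does not state a weighting for the difference; crude is only the natural reading. Randomisation is 1:1 in blocks within the same age and PAC-count strata. If the allocation is exactly equal in each stratum, Mantel-Haenszel weights are proportional to stratum size and the stratified difference equals the crude one. With small imbalances the two should stay close.

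**Conclusion.** The point holds as a defect of definition and reporting. Followed as written, SAP 4.2.2 would give a wrongly signed risk reduction for every new-onset SAT, AF or AFL end point, including four of the six key secondary end points, and an NNT that is the same for benefit and for harm. In the illustrations with an excess on memantine, the falsely positive reduction runs from +0.8 points (NNT 128) to +7.8 points (NNT 13). Those sizes rest on assumed counts out of 128 per arm; the sign error rests on the formula alone.

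The per-arm proportions and the RR with its CI would still show which arm did better. The CMH p values, the testing hierarchy, the primary analysis and the sample size are untouched. The missing CI for the difference is a smaller gap in the same paragraph, partly covered by the interval on the RR. The correction is worth making because the figures affected are the ones most likely to be quoted by themselves.

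**What to change.** Amend the paragraph on categorical end points in SAP 4.2.2 in three respects.

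1. Rename the measure risk difference (memantine minus placebo) and state beside each end point which sign favours memantine. Alternatively, keep ARR for the SAT, AF and AFL end points, defined as placebo minus memantine, and use absolute benefit, defined as memantine minus placebo, for the PAC and NSAT responder rates.
2. Label each NNT as to benefit or to harm according to the sign of the difference. Whether to print it when the interval includes zero is a matter of reporting preference; if it is printed, the interval should stand beside it.
3. Add a two-sided 95% CI for the difference and name the method, for example Mantel-Haenszel on the randomisation strata, which would also align the estimate with the CMH test.

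The cost is a change of wording and one more interval per categorical end point. It needs no new data and alters no test, error rate or sample size. If it is made after unblinding, it should be dated and recorded as a change of labelling and presentation.

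### SAP 4.2.2 calls memantine minus placebo an absolute risk reduction, so for new-onset SAT, AF and AFL the reported figure has the opposite sign to its name and the NNT is the same for benefit and harm

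*SAP*

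**What the plan says.** SAP 4.2.2 gives one reporting rule for all categorical secondary endpoints. By arm, "counts and proportions will be summarized by treatment group". On intervals: "Two-sided 95% CIs for incidence, cumulative incidence, or response rate will be calculated with the Clopper – Pearson method". The rule therefore covers both unfavourable events (incidence and cumulative incidence of arrhythmia) and favourable ones (response).

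For the comparison between arms: "The absolute risk reduction (ARR = incidence in the memantine group – incidence in the placebo group) will be reported". The same paragraph also requires a stratified CMH test and the relative risk (memantine divided by placebo) with its 95% CI, "together with the number needed to treat", which is defined as the reciprocal of the absolute value of the ARR.

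The endpoints under this rule are items d (new-onset SAT, AF or AFL at each window), e (cumulative new-onset AF) and g (PAC and NSAT responders) of SAP 4.2.2. Five of the six steps in the SAP 2.4 hierarchy are among them. Step a is "Week 6 responder rate for PACs ($\geq 50\%$ reduction"), a favourable outcome. Step c is "Cumulative incidence of new-onset AF from baseline to Week 8". Step d is "Incidence of new-onset AF at Week 4", and steps e and f repeat it for Weeks 6 and 8. Step b, NSAT burden, is continuous and falls outside the rule.

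Neither document gives a separate definition for unfavourable events or a number needed to harm. The protocol gives no ARR or NNT formula.

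**The concern.** The name and the formula disagree. A reduction in risk is how far the treated risk falls below the control risk, so it should be positive when treatment prevents the event. The SAP subtracts in the other order. If memantine prevents AF, the output labelled as a reduction is negative; if memantine causes AF, it is positive.

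The NNT adds to this. Taking the absolute value removes the sign, and no label replaces it, so an excess of AF on memantine would be given a number needed to treat that looks like a benefit.

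The SAP's own convention elsewhere points the other way. SAP 3.1.1 defines change as baseline minus post-baseline, so a fall in a participant's AF episode count is positive, whereas a fall in AF incidence under 4.2.2 is negative.

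What is at stake is how the AF results read. Four of the six hierarchy steps are AF incidences, and ARR and NNT are figures that are easily quoted without the rest of their row.

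**Working it through.** The plan states no numerical ARR or NNT, so there is no figure to reproduce. The check applies the SAP 4.2.2 formulas in both directions.

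**Inputs**
- Formulas, from SAP 4.2.2: ARR = p_M − p_P; NNT = 1/|ARR|; RR = p_M/p_P.
- Arm size: 128 per group (SAP 1.3.1), taking all randomized participants as dosed and so in the FAS.
- Event counts: assumed, because the documents give no AF rate. Two sizes of difference are shown, each with its mirror image.
- Responder proportions of 50% and 30%: also assumed. They are not the mean PAC reductions used in the sample-size section, although the numbers are the same.

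**Step 1. AF prevented, 4/128 against 10/128**
- ARR = (4 − 10)/128 = −6/128 = −0.0469, or −4.7 points.
- NNT = 128/6 = 21.3.
- RR = 4/10 = 0.4.

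**Step 2. AF caused, 10/128 against 4/128**
- ARR = +6/128 = +0.0469, or +4.7 points.
- NNT = 128/6 = 21.3.
- RR = 10/4 = 2.5.

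**Step 3. Other values**

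| Endpoint | Memantine | Placebo | True direction | SAP ARR (points) | SAP NNT | RR |
|---|---|---|---|---|---|---|
| AF | 4/128 | 10/128 | benefit | −4.7 | 21.3 | 0.40 |
| AF | 10/128 | 4/128 | harm | +4.7 | 21.3 | 2.50 |
| AF | 2/128 | 6/128 | benefit | −3.1 | 32.0 | 0.33 |
| AF | 6/128 | 2/128 | harm | +3.1 | 32.0 | 3.00 |
| PAC response | 50% | 30% | benefit | +20.0 | 5.0 | 1.67 |
| PAC response | 30% | 50% | harm | −20.0 | 5.0 | 0.60 |

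**Step 4. What is general.** The sign of p_M − p_P is opposite to that of a risk reduction at any two unequal rates, and 1/|p_M − p_P| does not change when the arms are exchanged. The pattern therefore does not depend on the assumed counts; only the sizes do. At equal rates the NNT is undefined, and the SAP has no rule for that case.

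**Step 5. What does not change.** The CMH test is computed from the stratified counts and does not use the ARR. The RR and the per-arm proportions are defined separately. In Step 2 the same output would also show 7.8% (10/128) against 3.1% (4/128) and an RR of 2.5, so the direction can be recovered.

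**The case against.** The strongest reply is that memantine minus placebo is an ordinary risk difference under the wrong name. The subtraction is openly defined and runs in the same direction as the RR beside it, and the absolute value in the NNT suggests that the authors expected negative values. Per-arm proportions and the RR with its CI are reported for the same endpoints, so a careful reader would not mistake a harm for a benefit. All of this stands, and it limits the point to labelling and reporting. It does not make the label right: the SAP says reduction, and neither document corrects that or says which sign favours memantine.

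A change of favourable sign between responder and AF endpoints is not an error in itself. Any difference taken in a fixed order behaves that way, as does the RR. It misleads here only because a single name, reduction, is used for both.

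A reader might infer more from the formula, but the documents do not support the following:
- **That the AF tests or the hierarchy are compromised.** SAP 2.4 proceeds on two-sided p values, which do not depend on the ARR. Whether a step should also require a difference in favour of memantine is a separate question that this formula neither creates nor settles.
- **That a pro-arrhythmic result would be concealed.** It would be mislabelled in the ARR and NNT figures, with the proportions and RR reported alongside.
- **That opposite meanings would appear in one table.** The SAP shows no table layout for these endpoints.
- **That the SAP overrides a correct protocol definition.** Protocol 7.3.2 gives the SAP precedence where the two differ, but the protocol has no ARR or NNT formula to differ from.

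**Conclusion.** The point holds as an error in a reported effect measure. As written, SAP 4.2.2 gives the figure called absolute risk reduction the wrong sign for its name in every new-onset SAT, AF or AFL comparison with a non-zero difference. That covers secondary endpoints d and e and hierarchy steps c to f. The NNT cannot separate benefit from harm for any categorical endpoint, including the responder rates.

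The direction of the error follows from the two definitions alone. Its size in this trial cannot be stated, because no AF rate is given; the 3.1 and 4.7 points and the NNTs of 32.0 and 21.3 are illustrations at assumed counts with 128 per arm. Type I error, power, p values and relative risks are not touched. It should be corrected before results are reported, because the wrong reading arises when the ARR or NNT is quoted without the proportions.

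**What to change.** In SAP 4.2.2, for all categorical endpoints:

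1. Replace the term absolute risk reduction (ARR) with risk difference (memantine minus placebo). The subtraction stays as it is and agrees in direction with the RR.
2. State the favourable direction for each endpoint: negative for new-onset SAT, AF and AFL, positive for the PAC and NSAT responder rates.
3. Label the reciprocal of the absolute risk difference as number needed to treat for benefit when the difference favours memantine and number needed to treat for harm when it does not. Add that it is not reported when the difference is zero.

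Reversing the subtraction for every endpoint would not do: it would move the fault to the responder rates, where memantine minus placebo already gives a benefit a positive sign. Reversing it for the arrhythmia endpoints only would leave two subtraction orders in one endpoint family and set the AF difference against the RR.

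The cost is a sentence or two of SAP text and the matching output labels. No new data are needed, and no test or hierarchy decision changes.

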1.3.2 Sample- Size Determination

Based on the results of our preliminary exploratory single-arm study evaluating the efficacy of memantine in the treatment of PACs, the 24-hour mean reduction in PACs was 75.4%. Considering the robustness of results from the small-sample trial and potential sampling error, we conservatively estimated a 50% reduction in the 24-hour mean burden of PACs following treatment with memantine, while the placebo group is expected to show a 30% reduction, with a standard deviation of 35%. The dropout rate is assumed to be 15.0%. Using EAST 6.5 software for sample size calculation with a one-sided $\alpha = 0.025$ and a 1:1 allocation ratio between the memantine and placebo groups, a total of 256 participants will be enrolled, providing more than 95% power to detect the pre-specified between-group difference.

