1.3.3 Randomization and Blinding

Eligible participants will be randomly assigned, in a 1:1 ratio, to receive either memantine or matching placebo. A stratified block design will be used, with randomization stratified by baseline 24-hour PAC burden (≥ 5000 vs. < 5000 PACs per 24 hours) and age (≥ 65 vs. < 65 years). An independent statistician who is otherwise unaffiliated with the study will generate the randomization list and corresponding treatment-allocation list with SAS software (version 9.4 or higher). Both lists will be uploaded to an interactive response technology (IRT) system, which will assign each participant a unique randomization number and the corresponding study-drug kit on Day 0. Randomization and kit numbers, once issued, will not be reused. Participants who withdraw from the study—irrespective of drug exposure—will not be re-enrolled.

2. General Statistical Considerations

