4.2.1 Primary Efficacy Analysis

The primary end point—the percent change from baseline in the 24-hour mean PAC count at Week 6—will be evaluated with an analysis- of- covariance (ANCOVA) model. Treatment group will be included as a fixed effect, and age and baseline 24-hour mean PAC count will be included as covariates. The between- group effect will be reported as the least- squares mean difference with its two- sided 95% confidence interval (CI) and p value.

Least- squares mean percentage reductions in the 24-hour mean PAC count will be plotted for each scheduled visit to depict response trajectories in both treatment groups.

Missing-Data Handling

Missing values for the Week 6 primary end point will be addressed with multiple imputation.

- **Imputation Procedure** Twenty complete data sets will be generated separately within each treatment group with a Markov chain Monte Carlo (MCMC) algorithm (PROC MI, SAS; seed = 20240716).

- **Imputation Model Covariates** Age, baseline 24-hour mean PAC count, and the 24-hour mean PAC count at every post-baseline visit.

After imputation, the data sets from both treatment groups will be combined. Each imputed data set will be analyzed with the prespecified ANCOVA model for the primary end point. Results will be pooled according to Rubin's rules with PROC MIANALYZE (SAS) to yield the final least-squares mean treatment difference with its two-sided 95% CI and P value.

Sensitivity Analysis:

A mixed-effects model for repeated measures (MMRM) will be applied to the primary end point as a prespecified sensitivity analysis. The model will include treatment group, visit, and the treatment-by-visit interaction as fixed effects and age and the baseline 24-hour mean PAC count as covariates. Parameters will be estimated with restricted maximum likelihood, and denominator degrees of freedom will be determined with the Kenward–Roger approximation.

Within-participant variability will be modeled with an unstructured covariance matrix. If the model fails to converge, alternative covariance structures will be evaluated sequentially—heterogeneous Toeplitz, heterogeneous first-order autoregressive, heterogeneous compound symmetry, Toeplitz, first-order autoregressive, and compound symmetry—until convergence is achieved; the first structure that converges will be retained.

Results will be presented as the least-squares mean treatment difference with the corresponding two-sided 95% CI.

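### The ANCOVA for NSAT burden and the other non-PAC continuous secondaries leaves out baseline PAC count, a stratification factor; if it predicts outcome beyond age and own baseline, power is lost needlessly

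*SAP*

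**What the plan says.** SAP 1.3.3 describes a blocked design "with randomization stratified by baseline 24-hour PAC burden" (cut at 5000 per 24 hours) and by age (cut at 65 years). The analyses use these factors as follows.

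- **Primary ANCOVA (SAP 4.2.1):** "age and baseline 24-hour mean PAC count will be included as covariates". The MMRM sensitivity analysis uses the same two covariates.
- **Categorical secondaries (SAP 4.2.2):** a Cochran–Mantel–Haenszel "test that uses the randomization strata", meaning both age and PAC count.
- **Continuous secondaries (SAP 4.2.2):** "The model will include treatment group as a fixed effect and age and the baseline value of the respective end point as covariates".

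Under the third rule, PAC count enters only where it is itself the end point. It is absent for NSAT episode count and burden, for SAT, AF and AFL episode counts and for the SF-36 score. No reason is given for keeping age and dropping PAC count.

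One of the affected end points is confirmatory. Item b of the testing hierarchy in SAP 2.4 is "Change from baseline to Week 6 in NSAT burden", tested at two-sided 0.05. The rule there is "If any endpoint fails to achieve significance, formal hypothesis testing will stop", and four new-onset AF end points follow. For continuous secondaries nothing is imputed: "participants lacking data at a given visit will be omitted from" the analysis of that visit.

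**The concern.** Stratified randomization balances PAC count between the arms, which lowers the true variance of the treatment estimate if PAC count predicts the outcome. A model without that factor leaves its variation in the residual, so the reported standard error is larger than the true one. The interval is then too wide and the test rejects less often than its nominal level. The design has paid for precision that the analysis does not collect.

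What is at stake is power at NSAT burden, and through the stopping rule the chance of formally testing the four AF end points. The documents give no effect size, SD or power for NSAT burden, so nothing shows that there is power to spare.

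**Working it through.** **The plan's own figure.** The only stated power, above 95%, is for the primary end point. Inputs are reductions of 50% and 30%, SD 35, one-sided 0.025, and 128 per arm with 15% dropout, so 128 × 0.85 = 108.8 evaluable per arm. With 109 per arm, 20 / (35 × √(2/109)) = 4.22 and Φ(4.22 − 1.96) = 98.8%; with 108 it is 98.7%. The claim reproduces. It says nothing about NSAT burden.

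**Closed form for the omission.** Let r be the correlation between PAC stratum and outcome that remains after age and the end point's own baseline. The documents do not give r; the range 0 to 0.5 is an assumption. With the stratum balanced by design:

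- Reported SE / true SE = 1/√(1 − r²).
- Effective critical value c = 1.96/√(1 − r²).
- Actual two-sided type I error = 2 × (1 − Φ(c)).
- Power of a test that would have 80% if adjusted = Φ(2.80 − c), where 2.80 = 1.96 + 0.84.

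| r | CI too wide by | Type I error | Power |
|---|---|---|---|
| 0 | 0% | 5.0% | 80.0% |
| 0.1 | 0.5% | 4.9% | 79.7% |
| 0.2 | 2.1% | 4.5% | 78.8% |
| 0.3 | 4.8% | 4.0% | 77.2% |
| 0.4 | 9.1% | 3.2% | 74.6% |
| 0.5 | 15.5% | 2.4% | 70.5% |

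**Which r is plausible.** If the strata split 50:50 (an assumption), the gap between them in within-stratum residual SDs is 2r/√(1 − r²). That is 0.63 SD at r = 0.3 and 1.15 SD at r = 0.5. Gaps this large, after age and own baseline are in the model, become hard to believe towards the upper end, so 0 to 0.3 is the more credible part.

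**Simulation with the stratum as the omitted factor.** 256 participants were randomized in permuted blocks within four strata, with 15% random dropout and observed cases only (about 218 analysed). There were 6000 null and 4000 power trials per r.

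| r | Type I error without / with stratum | Power without / with stratum |
|---|---|---|
| 0 | 5.1 / 5.0% | 79.7 / 79.8% |
| 0.1 | 5.1 / 5.1% | 79.3 / 79.6% |
| 0.2 | 4.9 / 5.0% | 78.5 / 79.8% |
| 0.3 | 3.9 / 4.6% | 76.2 / 79.8% |
| 0.4 | 3.6 / 4.9% | 73.2 / 78.8% |
| 0.5 | 2.8 / 4.8% | 69.2 / 79.4% |

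Monte Carlo SE is 0.3 points for type I error and 0.6 to 0.7 for power. The pattern agrees with the closed form. At r = 0 the extra term changes the SE by 0.03%.

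**Second simulation, with PAC count continuous.** Here 216 participants were analysed in blocks of 4, strata were cut at the median, the correlation between baseline PAC count and baseline NSAT was 0.3 or 0.6, and each cell had 4000 runs. The effect was set so that the written model has about 80% power. Written model against model with PAC count:

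- Partial R² 0.05: 79% against 81%.
- Partial R² 0.10: 80% against 83%.
- Partial R² 0.20: 80–81% against 87–88%.

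Under the null the written model rejected 4.3–5.1%, 4.3–4.6% and 3.3–4.0% respectively. Adding only the binary stratum recovered part of the gain: at least (80.975 − 79.625)/(83.225 − 79.625) = 38% and at most (80.125 − 79.05)/(80.70 − 79.05) = 65%.

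**The case against.** The strongest reply is that nothing here is an error. The written model is pre-specified and valid, and it already holds age and the end point's own baseline, which probably carries most of the prognostic information. PAC count helps only through what it adds beyond these, the documents do not say how much that is, and zero is possible. All of this stands, and it is why the point is one of efficiency and consistency.

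The size can also be pressed downward. The 50:50 split at 5000 PACs is the least favourable case for the written model. For the same 0.63 SD gap the loss is 2.8 points at 50:50, 2.3 at 70:30, 1.8 at 80:20 and 1.0 at 90:10; for a 0.3 SD gap it is at most 0.6. The further loss at the AF tests is smaller again, since it counts only if the primary and PAC responder tests succeed and the AF tests would themselves have succeeded. These are fair limits on the size and do not change its direction.

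Two other points stand in part. The primary ANCOVA names the PAC count, whereas the CMH tests use the 5000-beat stratum, so a fix should name one form. And SAP version 2.0 records that enrolment was nearly complete at the planned interim time point, so another change to a confirmatory model comes late. That calls for a dated, blinded amendment; it is no reason to forgo the change while the trial is blinded.

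**Conclusion.** The point holds as a low-severity recommendation. The omission is clear in the text and unexplained, and it runs against the plan's own practice for the primary and categorical end points. It causes no bias, does not inflate type I error, and leaves the primary analysis and its power untouched.

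The size rests on two assumptions the documents cannot settle: the residual correlation r, and 80% adjusted power at NSAT burden. On these, the loss is 0 to 3 power points for r up to 0.3 and about 10 points at r = 0.5. Confidence is high about the omission and its direction, and much lower about where r lies.

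**What to change.** In SAP 4.2.2, add baseline 24-hour mean PAC count as a covariate in the ANCOVA for every continuous secondary end point whose own baseline is not the PAC count. NSAT burden at Week 6 is the priority. The count is preferable to the binary stratum because it matches the primary model and recovered more of the gain in simulation; either is sound, but the SAP should name one. It should also state whether the PAC burden model is included, since its own baseline is the burden and not the count.

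The cost is one sentence and one degree of freedom per model, using data already collected for randomization. If PAC count turns out to have no residual value, the simulated cost is about 0.1 power point or less.

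The change must be documented before unblinding. If unblinding has already taken place, keep the written model for the formal test and report the PAC-adjusted model as a labelled sensitivity analysis.
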